## **1.5. Information About GS-9883/Emtricitabine/Tenofovir Alafenamide (GS-9883/F/TAF)**

Please refer to the GS-9883/F/TAF Investigator's Brochure for further information.

### **1.5.1. GS-US-141-1233: Relative Bioavailability of GS-9883, FTC, and TAF Between GS-9883/F/TAF and GS-9883 + F/TAF**

Study GS-US-141-1233 is a Phase 1, open-label, 2-cohort, multiple-period, fixed-sequence, crossover study conducted at a single center in the US to evaluate 1) the relative bioavailability (BA) of 2 GS-9883/F/TAF (75/200/25 mg and 50/200/25 mg) FDC tablets compared with the GS-9883 (75 mg) tablet and the F/TAF (200/25 mg) FDC tablet administered simultaneously and 2) the effect of food on the PK of GS-9883, FTC, and TAF when administered as GS-9883/F/TAF (75/200/25 mg and 50/200/25 mg) FDC tablets.

Cohort 1 evaluated the relative BA and food effect of GS-9883/F/TAF (75/200/25 mg) FDC tablet in a 3-period sequence. Following review of preliminary data from Cohort 1, Cohort 2 was added to the study via protocol amendment. Cohort 2 evaluated the relative BA and food effect of GS-9883/F/TAF (50/200/25 mg) FDC tablet in a 4-period sequence.

#### **Cohort 1 Results:**

##### Pharmacokinetic Results

Under fasted conditions, GS-9883 AUCinf and Cmax were 27% and 31% higher, respectively, following GS-9883/F/TAF (75/200/25 mg) FDC administration than following administration of single-agent GS-9883 (75 mg) with the F/TAF (200/25 mg) FDC. FTC and TAF exposure was similar following administration of GS-9883/F/TAF (75/200/25 mg) or single-agent GS-9883 (75 mg) with the F/TAF (200/25 mg) FDC. Compared with administration under fasted conditions, administration of the GS-9883/F/TAF (75/200/25 mg) FDC with a high-fat meal resulted in a 46% higher GS-9883 AUCinf and a 27% higher GS-9883 Cmax. The impact of food on TAF and FTC exposure was similar to that previously observed for F/TAF (Study GS-US-311-1386). GS-9883/F/TAF may be taken without regard to food. Based on these results, Cohort 2 was added to the study via protocol amendment to evaluate the relative BA of the GS-9883/F/TAF (50/200/25 mg) FDC tablet compared with the single-agent GS-9883 (75 mg) tablet and the F/TAF (200/25 mg) FDC tablet administered simultaneously.

## Safety Results

Of the 28 subjects included in the Safety Analysis Set for Cohort 1, 12 subjects (43%) had at least 1 treatment-emergent AE. All treatment emergent AEs were assessed as Grade 1 or 2 in severity. No deaths or other SAEs occurred during this study, and no subject discontinued the study due to an AE.

## **Cohort 2 Results:**

### Pharmacokinetic Results

The PK results from Study GS-US-141-1233 demonstrated that the GS-9883 AUCinf and Cmax following administration of the GS-9883/F/TAF (50/200/25 mg) FDC tablets was 79% and 78%, respectively of those observed in the same study following co-administration of GS-9883 75 mg single agent with F/TAF (200/25 mg) under fasted conditions. The GS-9883 exposures of 50/200/25 mg and 75/200/25 mg fixed dose combination tablets were approximately dose proportional under fasted and fed conditions, and a high fat and moderate fat meal had similar impact on GS-9883 in the 50/200/25 mg FDC with AUCinf increasing by 24%. The steady state paIQ95 of GS-9883/F/TAF (50/200/25 mg) following multiple doses was predicted to be 17 (fasted)-23 (fed). The exposures of TAF and FTC following administration of the GS-9883/F/TAF (50/200/25 mg) FDC were similar to those of GS-9883 75 mg single agent with F/TAF FDC, and the food effect on TAF and FTC in the GS-9883/F/TAF (50/200/25 mg) FDC was similar to historical results.

## Safety Results

Of the 28 subjects included in the Safety Analysis Set for Cohort 2, 12 subjects (43%) had at least 1 treatment-emergent AE. All treatment emergent AEs were assessed as Grade 1 or 2 in severity. No deaths or other SAEs occurred during this study, and no subject discontinued the study due to an AE.

### **1.6. EVG/COBI/FTC/TDF (E/C/F/TDF or Stribild®)**

Further information is available in the US Prescribing Information and Investigator's Brochure for E/C/F/TDF.

### **1.7. Emtricitabine/Tenofovir Disoproxil Fumarate (FTC/TDF, Truvada®)**

Further information is available in the Prescribing Information for Truvada®.

### **1.8. Ritonavir (RTV, /r, Norvir®)**

Further information is available in the Prescribing Information for Norvir®.

### **1.9. Atazanavir (ATV, Reyataz®)**

Further information is available in the Prescribing Information for Reyataz®.

## **1.10. Rationale for This Study**

HIV standard of care has relied upon nucleos(t)ide backbones for effective and durable virologic suppression, but nucleos(t)ide-associated toxicities are increasingly important as HIV-infected patients are often diagnosed earlier, initiate therapy earlier, and look toward lifelong therapy (often greater than 50 years). Where patients have access to treatment, morbidity and mortality are driven by non-AIDS-associated comorbidities, which are observed earlier than in HIV-uninfected age-matched controls despite the best available ART. The contribution of specific nucleos(t)ides, including abacavir and tenofovir disoproxil fumarate, to long-term morbidity and mortality is increasingly important in this context.

The GS-9883/F/TAF FDC has the potential to offer a simple, once-daily regimen containing a second generation INSTI that provides a high barrier to resistance, does not require a boosting agent, and offers an effective and safer alternative to standard nucleos(t)ide based regimens, without the need for HLA testing or close monitoring of renal or bone toxicities. It could provide an FDC treatment that avoids the risk of hypersensitivity reactions, would not contribute to an increased risk of cardiovascular events, could be used in patients with chronic hepatitis B or C infection or renal impairment, and that could be continued as patients age and confront non-HIV-related comorbidities. Approximately 50% of the global population of HIV-infected persons are women, however they remain under-represented in most clinical HIV studies. In general, studies to date have not shown gender differences in virologic responses to antiretroviral therapy (ART), but a number of studies have suggested that gender may influence the frequency, presentation, and severity of selected ARV-related adverse events. Although data are limited, the pharmacokinetics for some ARV drugs may differ between men and women, possibly because of variations in factors such as body weight, plasma volume, gastric emptying time, plasma protein levels, CYP450 activity, drug transporter function, and excretion activity. It is important to understand potential gender-specific safety and efficacy issues in women when assessing virologic response, tolerability, and adherence. This study will ensure that there is adequate safety data in HIV-1-infected women in the Phase 3 program for GS-9883/F/TAF.

The objective of this study is to evaluate the safety and efficacy of an FDC containing GS-9883/F/TAF versus continuing on a regimen consisting of E/C/F/TAF, E/C/F/TDF or ATV+RTV+FTC/TDF in women who are virologically suppressed. Switching to GS-9883/F/TAF offers the advantages of a single-tablet FDC containing the unboosted, next-generation INSTI, GS-9883, combined with a TAF-based nucleotide backbone. GS-9883/F/TAF FDC which includes TAF, has the potential to offer an effective and safer alternative to standard nucleos(t)ide based regimens, without the need for close monitoring of renal or bone toxicities or increase risk of cardiovascular complications as patients age and confront non HIV-related comorbidities.

## **1.11. Risk/Benefit Assessment for the Study**

All patients with HIV-1 infection should receive effective anti-retroviral therapy. Potential risks associated with all classes of ARVs include immune reconstitution syndrome, lipodystrophy, and lactic acidosis with steatosis. The risk of class effects is considered to be low. Important identified risks appropriately managed by study inclusion/exclusion criteria as well as through

close clinical and laboratory monitoring during the study are as follows: allergy to any components of the tablets. Protease inhibitors may be associated with increased lipid levels and gastrointestinal side effects. If patients are currently infected with hepatitis B and discontinue their existing or new therapy, there is a risk of severe acute exacerbations of hepatitis B. Interim data will also be reviewed by an independent data monitoring committee. Potential benefits of GS-9883/F/TAF may include provision of a new antiretroviral therapy that is not currently available and which may have fewer side effects than alternative therapies. Other potential benefits include provisions of fixed dose combination therapy, and the knowledge that patient participation will contribute to the body of knowledge of HIV therapies.

Following a chronic 39 week study in monkeys, animals administered the highest dose of GS-9883 (1000 mg/kg/day) had bile duct hyperplasia (increased cell growth) and hypertrophy (increased cell size), and some increased cell growth and inflammation in nearby liver cells. These effects were not seen in monkeys administered the mid-level dose (200 mg/kg/day), and these animals had plasma GS-9883 exposures that were approximately 5-fold above human exposures when given the GS-9883/F/TAF FDC. No adverse drug reactions associated with liver or bile duct problems has been identified in humans treated with GS-9883.

Potential hepatobiliary toxicity is appropriately managed by study inclusion/exclusion criteria, close clinical and laboratory monitoring, as well as specific toxicity management guidance to investigators (Refer to Section 7.5.4).

The overall benefit-risk assessment for GS-9883/F/TAF is favorable at this time.

## **1.12. Rationale for Dose Selection**

### FTC

The 200 mg dose of FTC represents the marketed dose for this agent that is currently available as single agent capsules (EMTRIVA) and as a component of a number of fixed-dose combination tablets, including: TRUVADA, ATRIPLA, COMPLERA (EVIPLERA), and STRIBILD.

### TAF

Based upon results of the Phase 1 Study GS-US-120-0104, in which various doses of TAF (8 mg, 25 mg, and 40 mg) were administered to HIV-infected subjects in 10 days of monotherapy, the range of exposure achieved with TAF 25 mg was chosen as the reference exposure. In this study, TAF 25 mg resulted in near-maximal antiviral activity and plasma TFV exposure > 90% lower relative to TDF.

The recommended dose of TAF is based on ensuring that patients have a TAF systemic exposure that is within the range of the reference exposure achieved with TAF 25 mg, or with TAF 10 mg when administered with the boosting agent COBI as E/C/F/TAF, for which an extensive safety and efficacy database exists. Specifically, TAF 25 mg is recommended with third agents that do not have a clinically relevant effect on TAF exposure. Study GS-US-141-1418 showed that GS-9883 does not have a clinically relevant effect on TAF exposure. Therefore, the dose of TAF 25 mg is appropriate for the GS-9883/F/TAF FDC.

## GS-9883

The dose of GS-9883 for Phase 2 was selected based upon data from Study GS-US-141-1219 ([Table 1-5](#)), in which HIV-1-infected subjects were administered 5, 25, 50, or 100 mg doses of GS-9883 monotherapy under fasting conditions for 10 days.

**Table 1-5.** **GS-US-141-1219: Trough GS-9883 Plasma Concentrations at Steady State Following GS-9883 Administration Under Fasting Conditions and Corresponding Protein-Adjusted  $\text{paIQ}_{95}$  Values**

GS-9883 Dose	N	Median (range) $C_{\text{tau,SS}}$ (ng/mL)	Median (range) $\text{paIQ}_{95}^a$
5 mg	4	206.5 (146.0 – 342.0)	1.3 (0.9 – 2.1)
25 mg	4	797.5 (714.0 – 1900.0)	4.9 (4.4 – 11.7)
50 mg	4	2170.0 (852.0 – 3020.0)	13.4 (5.3 – 18.6)
100 mg	4	4190.0 (3730.0 – 5970.0)	25.9 (23 – 36.9)

a The  $\text{paIQ}_{95}$  value is estimated based on steady-state  $C_{\text{tau}}$  values and the in vitro  $\text{paIC}_{95}$  value for wild-type HIV-1 (162 ng/mL).

Source: Data on File

Single-agent GS-9883 was well tolerated at all doses administered. The range of GS-9883 plasma exposure at steady state ( $C_{\text{tau,SS}}$ ) observed in the 50-mg cohort correlated with protein adjusted 95% inhibitory quotient ( $\text{paIQ}_{95}$ ) values ranging from 5.3 to 19, while the range of GS-9883 plasma exposure at steady state ( $C_{\text{tau,SS}}$ ) observed in the 100-mg cohort correlated with  $\text{paIQ}_{95}$  values ranging from 23 to 37 ([Table 1-5](#)).

Based on PK/PD analyses, exposure following a 75-mg dose of single-agent GS-9883 is expected to provide near-maximal virologic response, with a predicted  $\text{paIQ}_{95}$  of approximately 20, providing considerable coverage above the target concentration of 162 ng/mL ( $\text{paIC}_{95}$ ). GS-9883 (75 mg) single agent coadministered with F/TAF (200/25 mg) is currently being evaluated in a Phase 2 study, GS-US-141-1475 (GS-9883+F/TAF vs DTG+F/TAF). The Week 24 interim data from this study, support the safety and efficacy of GS-9883 exposures obtained with the 75 mg dose of the single agent.

## **GS-9883/F/TAF FDC Dose Selection**

A fixed dose formulation of GS-9883/F/TAF was developed for use in Phase 3 studies. Preliminary results from the relative bioavailability (rBA) study (GS-US-141-1233) of GS-9883/F/TAF (75/200/25 mg) showed that GS-9883 plasma exposure was higher (with  $C_{\text{max}}$  and  $\text{AUC}_{\text{inf}}$  increase of 31% and 27%, respectively) following administration of the FDC as compared with exposure following administration of GS-9883 (75 mg) + F/TAF (200/25 mg) under fasted conditions. The increase in GS-9883 exposures associated with the FDC formulation results in an estimated mean  $\text{paIQ}_{95}$  of 24.3, compared to an estimated mean  $\text{paIQ}_{95}$  of 19.2 for the GS-9883 (75 mg) single agent coadministered with F/TAF, in the fasted state.

In order to bridge exposures of GS-9883 in the FDC to the exposure observed with GS-9883 75 mg administered as a single agent, and to bridge to the safe and effective exposures observed in the Phase 2 study GS-US-141-1475, a lower strength GS-9883/F/TAF FDC was developed for use in the Phase 3 studies. Comparability of GS-9883 exposures was confirmed in an rBA study of GS-9883/F/TAF (50/200/25 mg) and GS-9883 (75 mg) + F/TAF prior to initiation of dosing in the Phase 3 studies.

#### **E/C/F/TAF**

EVG/COBI/FTC/TAF (150/150/200/10 mg) is a fixed dose combination, with only one dose combination available; and has been approved by the United States Food and Drug Administration (FDA) for the treatment of human immunodeficiency virus type 1 (HIV-1) infection in adults and pediatric patients 12 years of age and older with no ARV treatment history or to replace the current ARV regimen in those who are virologically suppressed on a stable ARV regimen with no history of treatment failure and no known substitutions associated with resistance. This FDC contains the equivalent doses of EVG, COBI and FTC in the marketed product, Stribild® (STB).

#### **E/C/F/TDF (STB)**

EVG/COBI/FTC/TDF (150/150/200/300 mg) is a fixed dose combination, with only one dose combination available; and is approved for use (Stribild®) in the United States by the Food and Drug Administration (FDA), for the treatment of HIV-1 infection in treatment-naïve adults.

#### **ATV+RTV+FTC/TDF**

ATV (300 mg), RTV (100 mg) and FTC/TDF (200/300 mg) represent the current marketed doses of these products.

#### **1.13. Compliance**

This study will be conducted in compliance with this protocol, Good Clinical Practice (GCP), and all applicable regulatory requirements.

## **2. OBJECTIVES**

The primary objective of this study is:

- To evaluate the efficacy of switching to an FDC of GS-9883/F/TAF versus continuing on a regimen consisting of E/C/F/TAF, E/C/F/TDF or ATV+RTV+FTC/TDF in virologically suppressed HIV-1 infected women as determined by the proportion of subjects with HIV-1 RNA  $\geq$  50 copies/mL at Week 48.

The secondary objective of this study is:

- To evaluate the safety and tolerability of the treatment groups through Week 48.

### 3. STUDY DESIGN

#### 3.1. Endpoints

The primary endpoint of this study is:

- The proportion of subjects with HIV-1 RNA  $\geq$  50 copies/mL at Week 48 as determined by the US FDA-defined snapshot algorithm.

The secondary endpoints include:

- The proportion of subjects with HIV-1 RNA  $<$  50 copies/mL at Week 48 as determined by the US FDA-defined snapshot algorithm.
- The change from baseline in CD4+ cell count at Week 48.

#### 3.2. Study Design

This protocol describes a randomized, open label, multicenter, active-controlled study to evaluate the safety and efficacy of switching to a GS-9883/F/TAF FDC in HIV-1 infected women who are virologically suppressed (HIV-1 RNA  $<$  50 copies/mL) on a regimen consisting of E/C/F/TAF, E/C/F/TDF, or ATV+RTV+FTC/TDF for  $\geq$  12 consecutive weeks prior to screening.

#### 3.3. Study Treatments

Subjects who complete the following criteria will be given the option to participate in this study:

- Completion of the Week 48 OLE visit or any post Week 48 OLE visits in study GS-US-236-0128, or
- Completion of the Week 96 visit or any post Week 96 visits in study GS-US-292-0109, or
- Completion of the Week 144 visit or any post Week 144 visits in studies GS-US-292-0104 or GS-US-292-0111

Subjects who provide written informed consent and meet all eligibility criteria will be randomized in a 1:1 ratio to receive open label medication:

[figure not shown]
- **Treatment Group 1:** FDC of GS-9883 50 mg/emtricitabine 200 mg/tenofovir alafenamide 25 mg (GS-9883/F/TAF) administered orally, once daily, without regard to food (approximately n = 235)
- **Treatment Group 2:** Stay on baseline regimen (SBR), including E/C/F/TAF, E/C/F/TDF or ATV+RTV+FTC/TDF administered orally, once daily, with food (approximately n = 235)

### 3.4. Duration of Treatment

Subjects will be treated for at least 48 weeks. At the Week 48 Visit, subjects in a country where GS-9883/F/TAF FDC is not available will be given the option to receive GS-9883/F/TAF FDC for an additional 48 weeks and attend study visits every 12 weeks, or until the product becomes accessible to subjects through an access program, or until Gilead Sciences elects to discontinue the study in that country, whichever occurs first.

Subjects who complete the study through the Week 48 Visit and do not continue post Week 48 will be required to return to the clinic 30 days after the Week 48 Visit for a 30 Day Follow-Up Visit.

**Figure 3-1. Study Schema**

- a Following the Day 1 visit, subjects will be required to return for study visits at Weeks 4, 8, 12 and then every 12 weeks through Week 48
- b After Week 48, subjects in a country where GS-9883/F/TAF FDC is not available will be given the option to receive GS-9883/F/TAF for an additional 48 weeks, or until the product becomes accessible to subjects through an access program, or until Gilead Sciences elects to discontinue the study in that country, whichever occurs first
- c Subjects who complete the study through Week 48 and do not wish to receive GS-9883/F/TAF FDC will be required to return to the clinic 30 days after the completion of study drug for a 30-day follow-up visit

[figure not shown]
### 3.5. Biomarker Testing

#### 3.5.1. Biomarker Samples for Optional Future Research

PPD

The text 'PPD' is followed by a large blue rectangular redaction box that covers the majority of the page below it, indicating that the biomarker samples for optional future research are not present in the document.

PPD

## 4. SUBJECT POPULATION

### 4.1. Number of Subjects and Subject Selection

Approximately 470 subjects who meet the eligibility criteria will be enrolled.

### 4.2. Inclusion Criteria

Subjects must meet **all** of the following inclusion criteria to be eligible for participation in this study.

- 1) The ability to understand and sign a written informed consent form, which must be obtained prior to initiation of study procedures
- 2) Female, (at birth), Age  $\geq$  18 years
- 3) Currently on a stable antiretroviral regimen of E/C/F/TAF, E/C/F/TDF, or ATV+RTV+FTC/TDF continuously for  $\geq$  12 consecutive weeks preceding the screening visit
- 4) Completion of the Week 48 OLE visit or any post Week 48 OLE visits in study GS-US-236-0128, completion of the Week 96 visit or any post Week 96 visits in study GS-US-292-0109, or completion of the Week 144 visit or any post Week 144 visits in studies GS-US-292-0104 or GS-US-292-0111
- 5) Documented plasma HIV-1 RNA levels  $<$  50 copies/mL for  $\geq$  12 weeks preceding the Screening Visit. After reaching HIV-1 RNA  $<$  50 copies/mL, single values of HIV-1 RNA  $\geq$  50 copies/mL followed by resuppression to  $<$  50 copies/mL are allowed
- 6) HIV-1 RNA  $<$  50 copies/mL at screening
- 7) Normal ECG (or if abnormal, determined by the Investigator to be not clinically significant)
- 8) Adequate renal function:  
Estimated glomerular filtration rate  $\geq$  50 mL/min ( $\geq$  0.83 mL/sec) according to the Cockcroft-Gault formula [{Cockcroft et al 1976}](#):

$$\frac{(140 - \text{age in years}) \times (\text{wt in kg})}{72 \times (\text{serum creatinine in mg/dL})} \times 0.85 = \text{CrCL (mL/min)}$$

$$\frac{(140 - \text{age in years}) \times (\text{wt in kg}) \times 0.85}{72 \times (\text{serum creatinine in } \mu\text{mol/L}) \times 0.6786} = \text{CrCL (mL/sec)}$$

- 9) Hepatic transaminases (AST and ALT)  $\leq 5 \times$  upper limit of normal (ULN).
- 10) Total bilirubin  $\leq 1.5$  mg/dL ( $\leq 26 \mu\text{mol/L}$ ), or normal direct bilirubin.

- 11) Adequate hematologic function (absolute neutrophil count  $\geq 750/\text{mm}^3$  ( $\geq 0.75 \text{ GI/L}$ ); platelets  $\geq 50,000/\text{mm}^3$  ( $\geq 50 \text{ GI/L}$ ); hemoglobin  $\geq 8.5 \text{ g/dL}$  ( $\geq 85 \text{ g/L}$ )).
- 12) Serum amylase  $\leq 5 \times \text{ULN}$  (subjects with serum amylase  $> 5 \times \text{ULN}$  will remain eligible if serum lipase is  $\leq 5 \times \text{ULN}$ ).
- 13) Women of childbearing potential must agree to utilize protocol recommended highly effective contraceptive methods or be non-heterosexually active or practice sexual abstinence (as defined in [Appendix 6](#)) from screening, throughout the duration of the study period, and for 30 days following the last dose of study drug.
  - a) Women who utilize hormonal contraceptive as one of their birth control methods must have used the same method for at least 3 months prior to study drug dosing.
  - b) Female subjects who have stopped menstruating for  $\geq 12$  months but do not have documentation of ovarian hormonal failure must have a serum follicle stimulating hormone (FSH) level at screening within the post-menopausal range based on the Central Laboratory reference range.
- 14) Have no documented or suspected resistance to FTC, TFV, ATV or EVG including, but not limited to the reverse transcriptase resistance mutations K65R and M184V/I

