7.2.2.1. Treatment Emergent Laboratory Abnormalities

Treatment-emergent laboratory abnormalities are defined as values that increase at least 1 toxicity grade from baseline at any postbaseline time point, up to 30 days from the last dose date of B/F/TAF. If the relevant baseline laboratory value is missing, any abnormality of at least Grade 1 observed within the time frame specified above will be considered treatment-emergent.

Fasting glucose and nonfasting glucose (including glucose results without a known fasting status) are graded based on different grading scales as specified in the protocol.

Treatment-emergent laboratory abnormalities will be summarized for fasting glucose. Maximum postbaseline grade, instead of treatment-emergent grade, for nonfasting glucose (including glucose results without a known fasting status) will be summarized, as nonfasting glucose was not assessed at baseline visit for most of the subjects; therefore, an abnormality is treatment-emergent or not cannot be determined for these subjects.

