7.2.4. Liver-Related Laboratory Evaluations

Liver-related abnormalities after initial study drug dosing will be examined and summarized using the number and percentage of subjects who were reported to have the following laboratory test values for postbaseline measurements collected in the all B/F/TAF phase of this study:

- Aspartate aminotransferase (AST): (a) $> 3 \times \text{ULN}$, (b) $> 5 \times \text{ULN}$, (c) $> 10 \times \text{ULN}$, (d) $> 20 \times \text{ULN}$
- Alanine aminotransferase (ALT): (a) $> 3 \times \text{ULN}$, (b) $> 5 \times \text{ULN}$, (c) $> 10 \times \text{ULN}$, (d) $> 20 \times \text{ULN}$
- AST or ALT: (a) $> 3 \times \text{ULN}$, (b) $> 5 \times \text{ULN}$, (c) $> 10 \times \text{ULN}$, (d) $> 20 \times \text{ULN}$
- Total bilirubin: (a) $> 1 \times \text{ULN}$, (b) $> 2 \times \text{ULN}$
- Alkaline phosphatase (ALP) $> 1.5 \times \text{ULN}$
- AST or ALT $> 3 \times \text{ULN}$ and total bilirubin: (a) $> 1.5 \times \text{ULN}$, (b) $> 2 \times \text{ULN}$
- AST or ALT $> 3 \times \text{ULN}$ and total bilirubin $> 2 \times \text{ULN}$ and ALP $< 2 \times \text{ULN}$

The summary will include data from all postbaseline visits up to 30 days after the last dose date of B/F/TAF. For individual laboratory tests, subjects will be counted once based on the most severe postbaseline value. For both the composite endpoint of AST or ALT and total bilirubin, and the composite endpoint of AST or ALT, total bilirubin, and ALP, subjects will be counted once when the criteria are met at the same postbaseline visit date. The denominator is the number of subjects in the All B/F/TAF Analysis Set with nonmissing postbaseline value of the tests in evaluation at the same postbaseline visit date.

Subjects with AST or ALT $> 3 \times \text{ULN}$ will also be listed.

In addition, baseline, postbaseline, and change from baseline in AST, ALT, ALP, and total bilirubin will be summarized by treatment group and visit using descriptive statistics.

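### The SAP 7.2.4 liver threshold table has no baseline reference, so stable elevations that the entry criteria allow can be counted alongside new ones; a baseline shift table would separate them (minor)

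*Protocol*

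**What the plan says.** **Entry.** Protocol 4.2 criterion 9, which begins "Hepatic transaminases (AST and ALT", caps AST and ALT at 5 × ULN. Criterion 10 asks for total bilirubin of at most 1.5 mg/dL, "or normal direct bilirubin", so total bilirubin has no ceiling when the direct fraction is normal.

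**Extension.** Protocol 3.4 and 6.5.1 offer B/F/TAF after Week 48 in some countries and restate no transaminase or bilirubin limit. SAP 3.2 and 3.8.1 reset baseline for women moving from SBR to the last value on or before their first B/F/TAF dose.

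**Threshold table.** SAP 7.2.4 states: "Liver-related abnormalities after initial study drug dosing will be examined and summarized using the number and percentage of subjects". Its rows are AST, ALT, and AST or ALT above 3, 5, 10 and 20 × ULN; total bilirubin above 1 and 2 × ULN; ALP above 1.5 × ULN; and composites of AST or ALT above 3 × ULN with bilirubin, one of which also requires ALP below 2 × ULN. On counting: "For individual laboratory tests, subjects will be counted once based on the most severe postbaseline value". The composites must be met on one visit date. No row carries a baseline condition.

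**Baseline used elsewhere.** The same section says that "baseline, postbaseline, and change from baseline in AST, ALT, ALP, and total bilirubin will be summarized by treatment group and visit", and it lists women with AST or ALT above 3 × ULN. SAP 7.2.2.1 adds: "Treatment-emergent laboratory abnormalities are defined as values that increase at least 1 toxicity grade from baseline at any postbaseline time point". SAP Appendix 5 includes AST, ALT and total bilirubin in those graded tables.

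**Comparator.** SAP 2.3 and 3 restrict the final tables and figures to B/F/TAF data.

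**The concern.** Hepatobiliary toxicity is the risk that the protocol singles out from the 39-week monkey study (1.11 and 7.5.4), and 7.5.4 says that the risk to humans is not known. SAP 7.2.4 is the part of the final analysis that applies the 3 × ULN and combined transaminase-bilirubin thresholds to that question. With no concurrent control in the final tables, a woman's own baseline is the only reference for deciding whether a value is new.

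The entry rules make pre-existing elevation possible. Protocol 4.3 excludes recent acute hepatitis and decompensated cirrhosis. Chronic hepatitis B and C are screened for and monitored but are not excluded. Protocol 7.5.6 notes that most patients on atazanavir have raised indirect bilirubin. Without a baseline column, the percentage in a row mixes women who crossed the threshold on B/F/TAF with women who were already above it.

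**Working it through.** The plan gives no figure for this point, so the check classifies example values under both rules.

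**Inputs.** The SAP 7.2.4 cuts are listed above. The AST/ALT grades in Protocol Appendix 4 are Grade 1, 1.25 to 2.50; Grade 2, > 2.50 to 5.00; Grade 3, > 5.00 to 10.00; Grade 4, > 10.00 × ULN. The bilirubin grades are Grade 1, > 1.0 to 1.5; Grade 2, > 1.5 to 2.5; Grade 3, > 2.5 to 5.0; Grade 4, > 5.0 × ULN. Treatment-emergent means a rise of at least one grade.

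**AST or ALT (× ULN)**

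| Baseline | Worst on drug | 7.2.4 rows entered | Grade | Treatment-emergent |
|---|---|---|---|---|
| 4.0 | 4.0 | > 3 | 2 to 2 | no |
| 5.0 | 3.2 | > 3 | 2 to 2 | no |
| 2.0 | 3.2 | > 3 | 1 to 2 | yes |
| 2.6 | 4.9 | > 3 | 2 to 2 | no |
| 4.0 | 5.5 | > 3, > 5 | 2 to 3 | yes |

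The first two women are counted in 7.2.4 although nothing worsened; the second improved. The fourth crosses 3 × ULN for the first time, but the graded table misses her because 3 × ULN lies inside Grade 2. The new crossings missed are those that start above 2.5 and at or below 3 × ULN and stay at or below 5 × ULN. The 5 and 10 × ULN cuts are grade boundaries, so a woman crossing either from below is always treatment-emergent.

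**Bilirubin.** The 1 × ULN cut is the floor of Grade 1, so new crossings are treatment-emergent. The 2 × ULN cut lies inside Grade 2: a rise from 1.6 to 2.4 × ULN is Grade 2 to 2 and is not flagged.

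**Composites.** Take ALT 4 × ULN, total bilirubin 2.4 × ULN with normal direct bilirubin, and ALP below 2 × ULN, all unchanged. Criteria 9 and 10 admit her, and she enters the AST/ALT, bilirubin and ALP composite. Graded tables treat each test separately and cannot show whether the combination is new.

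**Which rows.** A woman whose baseline is within the entry limit and stable cannot enter the > 5, > 10 or > 20 × ULN rows. For a woman moving from SBR, criterion 9 does not cap the reset baseline. Protocol 7.5.5.1 also describes circumstances in which a woman with ALT above 10 × ULN may stay on study medication. A high baseline in that group is therefore not ruled out.

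**Size.** One woman is 1/235 = 0.43 percentage points. The documents do not say how many women have a baseline between 3 and 5 × ULN. Under an assumed proportion f:

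| f (assumed) | 235 × f | 470 × f |
|---|---|---|
| 0.2% | 0.5 | 0.9 |
| 0.5% | 1.2 | 2.4 |
| 1% | 2.4 | 4.7 |
| 2% | 4.7 | 9.4 |

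The 470 column is a ceiling for the combined B/F/TAF group, because it supposes that every SBR woman switches.

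**The case against.** The best reply is that the SAP already deals with most of this. The treatment-emergent tables use baseline, include AST, ALT and total bilirubin, and reproduce the 5 and 10 × ULN cuts and bilirubin > 1 × ULN. For 3 × ULN they miss only a narrow band of starting values. SAP 7.2 lists all chemistry results by subject in time order, and 7.2.4 lists women with AST or ALT above 3 × ULN, so a handful of cases can be read individually. Raised bilirubin from atazanavir may fall after the switch. All of this stands, and it is why the point is minor. It does not cover the exact 3 × ULN cut, bilirubin > 2 × ULN or the composites, and reading cases from a listing is not a tabulated result.

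A reader might infer more than the documents support:

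- **That these women are reported as treatment-emergent or drug-related.** SAP 7.2.4 describes abnormalities after dosing and uses neither label.
- **That every postbaseline value is counted.** Each woman counts once per individual test, on her worst value.
- **That the rate is inflated by a known multiple.** Assuming 0.5% to 2% stable elevation and 1% true new crossing would give 1.5% to 3.0%, or 1.5 to 3 times the true rate. None of these inputs is in the documents, and the multiple depends on the choice of 1%.
- **That the study has no comparative liver data.** SAP 2.2 and 3 place the SBR data in the Week 48 analysis. Its plan is not among the documents, so its liver tables cannot be judged.

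**Conclusion.** The gap is real but small. The 7.2.4 threshold rows cannot separate new from pre-existing elevation, and the graded tables close only part of that gap. What remains is the exact 3 × ULN cut, bilirubin > 2 × ULN, the composites, and women moving from SBR whose baseline has no stated limit. The conclusion needs only the wording of the criteria, the SAP rows and the grading scale. The number of women affected is unknown; the counts above rest on assumed proportions. The entry criteria are not at fault, and neither the primary analysis nor any inferential result changes. This is a cheap improvement of minor severity, worth making because it concerns the drug's named preclinical risk in an uncontrolled analysis.

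**What to change.** In SAP 7.2.4, keep all current rows and make three additions.

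1. For AST, ALT and total bilirubin, add a shift table of baseline category against worst postbaseline category, using the section's own cuts and a column for missing baseline. A count of new crossings among women at or below each threshold at baseline would also serve.
2. For each composite, count as new any woman who did not meet the full composite at baseline. Requiring only that the transaminase part was absent at baseline would drop a woman with chronic ALT of 4 × ULN who then develops bilirubin above 2 × ULN, a case the table should show.
3. Show baseline AST, ALT and total bilirubin in the listing of women with AST or ALT above 3 × ULN.

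Baseline should follow SAP 3.8.1. The values are already collected at or before the first B/F/TAF dose. The cost is one additional table and extra columns in one listing. If the SAP is already final, its Introduction provides for recording the change in the clinical study report.
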